Some patients present a particularly severe form of PIGFD. The most severely affected individuals described to date are those with Laron Syndrome, which was first identified in 1966 [13] and later documented to be caused by genetic mutations involving the GHR [14, 15]. Other molecular defects of the GHR, GH signalling cascade, or IGF-1 gene expression resulting in PIGFD have since been identified [7, 16]. The common feature in all children with these defects is extreme short stature. Epidemiological data show that severe primary insulin-like growth factor-1 deficiency (SPIGFD) is a rare condition with an estimated prevalence of less than 1 in 100,000 worldwide [17].

SPIGFD is defined in the European Union (EU) by:

- height SDS ≤ -3.0 and
- basal IGF-1 levels below the 2.5th percentile for age and gender and
- GH sufficiency.
- Exclusion of secondary forms of IGF-1 deficiency, such as malnutrition, hypopituitarism, hypothyroidism, or chronic treatment with pharmacologic doses of anti-inflammatory steroids.

The EU definition of SPIGFD includes patients with mutations in the GHR, post-GHR signalling pathway, and IGF-1 gene defects; they are not GH deficient, and therefore, they

cannot be expected to respond adequately to exogenous GH treatment. In some cases, when deemed necessary, the physician may decide to assist in the diagnosis by performing an IGF-1 generation test.

SPIGFD is defined in the United States of America (USA) by:

- height SDS ≤ -3.0 and
- basal IGF-1 SDS ≤ -3.0 and
- normal or elevated GH
- Exclusion of secondary forms of IGF-1 deficiency, such as GH deficiency, malnutrition, hypothyroidism, or chronic treatment with pharmacologic doses of anti-inflammatory corticosteroids.

In summary, growth failure in children with SPIGFD is a serious and chronically debilitating condition which, if untreated, can result in final adult height (FAH) 4 to 10 standard deviations (SDs) below average and a range of health conditions such as obesity, hyperlipidaemia, insulin resistance, muscle weakness and osteoporosis as well as short stature with thin bones and undeveloped muscles [18, 19].

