Increlex® received MA in the EU and the European Economic Area (including Iceland, Liechtenstein and Norway) under Exceptional Circumstances in August 2007 and is indicated for the long-term treatment of growth failure in children and adolescents from 2 to 18 years with confirmed SPIGFD. There is an ongoing Specific Obligation to complete certain post-authorisation measures, discussed in Section 7.3.

Although the prevalence of SPIGFD is low (less than 1 in 100,000 worldwide [17]), at present there is no licensed treatment available for this indication other than Increlex® (Somazon® in Japan), and Increlex® treatment offers the potential for life-long benefits in these patients. The safety profile of Increlex® is well known as the drug has been approved for more than 12 years in the EU and USA, and the benefit/risk ratio of Increlex® in this indication is considered to be favourable in respect of the approved label and the recommended dose. Nevertheless, the benefit-risk of the product is reviewed by the European Medicines Agency (EMA) on a yearly basis through the submission of yearly Periodic Safety Update Reports and annual reassessments of the licence.

Increlex® may increase the risk of benign and malignant neoplasias, particularly in case of off-label use and doses over the maximum dose tolerated. Increlex® is contraindicated in children and adolescents with active or suspected neoplasia, or any condition or medical history which increases the risk of benign or malignant neoplasia. Therapy should be discontinued if evidence of neoplasia develops.

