7.3 Rationale for the Registry

As the current knowledge of IGF-1 biology suggests that IGF-1 plays a role in malignancies in all organs and tissues, there is an increased risk of benign and malignant neoplasia in children and adolescents treated with Increlex®. In order to monitor the risk of neoplasms and other safety concerns such as metabolic or cardiovascular risk, and as part of the overall risk management strategy for Increlex®, the Marketing Authorisation Holder (MAH) put in place a post-authorisation safety surveillance registry in the EU, called the European Increlex® (Mecasermin [rDNA Origin] Injection) Growth Forum Database (EU-IGFD 2-79-52800-002) to monitor the safety and effectiveness of Increlex® therapy, with the Specific Obligation to investigate long-term safety until 5 years after the end of treatment for a subset of participants exposed for at least 3 years. The EU-IGFD registry was implemented at the end of 2008 in ten European countries with a MA approved for Increlex® under Exceptional Circumstances.

Recently, as a result of postmarketing safety surveillance activities, occurrences of benign and malignant neoplasia were observed among children and adolescents who received treatment with Increlex®. A safety signal was submitted to the EMA which concluded that the benefit-risk profile of Increlex® remains positive in its approved indication only, at doses not higher than the daily recommended doses. In May 2019, a Type II variation to update the EU Summary of Product Characteristics (SmPC), Risk Management Plan (RMP) and Additional Risk Minimisation Material was distributed in the EU and relevant global markets between December 2019 and July 2020.

Considering the identified risk of malignancies, the Specific Obligation to investigate long-term safety after the end of Increlex® treatment and the possible occurrence of malignancies as well as other risks, the MAH has decided:

- To geographically expand the current EU-IGFD registry to additional countries within and outside Europe where the product is registered and marketed, and;
- To collect long-term safety data after completion of treatment for all participants who have received treatment with Increlex®, regardless of duration of therapy.

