8.2 Objectives

8.2.1 Primary Objective

- To collect safety data in children and adolescents receiving Increlex® for the treatment of SPIGFD.

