9.2.1 Inclusion Criteria

(2) Children and adolescents from 2 to 18 years:

- For US, patients starting or planning to start or currently receiving treatment with Increlex® therapy for severe primary IGF-1 deficiency as defined by the US Increlex® prescribing information or for growth hormone (GH) gene deletion who have developed neutralizing antibodies to GH.
- For EU, patients starting or planning to start or currently receiving treatment with Increlex® therapy according to the locally approved product information. Note:

not applicable for patients enrolled in the EU-IGFD registry and entering or currently in the post-treatment period.

(2) Signed informed consent as per local regulations needs to be obtained. Parents or legally authorised representatives if applicable must give signed informed consent before any registry-related activities are conducted. Assent from the participant should also be obtained as appropriate.

9.2.2 *Exclusion Criteria*

(1) Patient currently participating in an Increlex® clinical trial.

(2) Patient currently participating in any clinical trial for growth retardation.

(3) Patient with any contraindication to Increlex® or any condition subject to special warning as per the locally approved label.

- For US patients, these include patients with hypersensitivity to the active substance or any of the excipients, patients with active or suspected neoplasia and patients with closed epiphyses.
- For EU patients: these include patients with hypersensitivity to the active substance or any of the excipients, patients with active or suspected neoplasia or any condition or medical history which increases the risk of benign or malignant neoplasia and patients with closed epiphyses. Note: not applicable for patients enrolled in the EU-IGFD registry and entering or currently in the post-treatment period.

Note: for any patients enrolled in the registry under previous inclusion/exclusion criteria (i.e. before implementation of Protocol Amendment #6), who would be ineligible according to any of the above inclusion or exclusion criteria, e.g. receiving Increlex® for an indication not covered by the locally approved product information, a letter will be sent to the Investigator to alert him/her about the off-label use of the product (specifically for the risk of neoplasias). The patient could continue to be followed up in the registry for safety data in the post-treatment period.

9.2.3 *Registry Population*

9.2.3.1 *Physician Profile*

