Eligible Investigators for the global registry will be:

- Physicians who are experienced in the diagnosis and management of children and adolescents with SPIGFD;
- Physicians located in a country where Increlex® is approved and marketed and where the study is implemented;
- Physicians who have prescribed/plan to prescribe Increlex® according to the locally approved product information.

9.2.3.2 *Participant Population*

Eligible participants will be children and adolescents from 2 to 18 years starting or planning to start or currently receiving treatment with Increlex® therapy for SPIGFD according to the locally approved product information in participating countries. In order to be enrolled, participants must comply with all the inclusion criteria (Section 9.2.1) and exclusion criteria (Section 9.2.2).

9.2.3.3 *Patient Screening and Number of Participants*

The current global Increlex® registry should be proposed to all eligible Increlex®-treated patients at the site.

During screening, Investigators must explain the purpose of the registry as well as the identified risk of neoplasia and the need to be followed up until at least 5 years after the end of treatment. Investigators must give the Participant Information Sheet (PIS) to the participant (and/or the participant's parents or legally authorised representative) which summarises all information related to the study given by Investigators:

- If participation in the registry is confirmed (the participant/parents or legally authorised representative agree to participation), the informed consent will be discussed and signed (before any related data collection) and the enrolment visit will be recorded.
- If the patient is not participating in the registry, registration date and reason for non-participation should be recorded in the eCRF in order to assess the proportion of non-included patients, only if the patient has no objection to this data collection.

A unique number will be attributed to each participant enrolled, to be used throughout the registry.

9.2.4 *Registry Duration*

9.2.4.1 *Recruitment Period*

This is an ongoing open-ended registry. Enrolment in the EU-IGFD registry started in December 2008.

For each new participating site/country, enrolment will start following local site initiation with all necessary regulatory and ethics local approvals.

9.2.4.2 *Treatment Duration*

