9.7 Data Analysis

9.7.1 Analyses Population Definitions

At the site level:

Screened: site which has been contacted for participation in the registry and confirmed that they are currently following patients who may be eligible for the registry (this includes both participating and non-participating sites).

Participating: site which has agreed to participate in the registry and has completed a patient screening log (as minimum data requested for participation).

At the patient/participant level:

Screened Population: all patients included in the patient screening log (this includes both enrolled and non-enrolled patients, with the reason for non-enrolment).

Enrolled Population: all participants who are fully informed about the registry and who have given their written informed consent to participate (and/or their parents/legally authorised representatives) before implementation of any registry-related procedure.

Registry Population: all participants who have completed at least one follow-up visit and who have taken the treatment at least once.

Complete Population: all participants who have stopped treatment and who have been followed until FAH reached.

Safety Population: all participants who have taken the treatment at least once and with at least one follow-up visit or presence of any post-study treatment safety data.

Long-term Safety Population: all participants who have been exposed to Increlex® for at least 3 years and who ended therapy at least 2 years prior to the collection of long-term safety data. The primary analysis based on the primary endpoint will be performed on the Safety Population.

9.7.2 *Statistical and Analytical Methods*

9.7.2.1 *Statistical Analyses*

The statistical analyses will be performed by an external SP managed by the Sponsor.

A Statistical Analysis Plan (SAP) describing the planned statistical analysis in detail with tables, figures and listings templates will be developed as a separate document.

Statistical evaluation will be performed using Statistical Analysis System (SAS)[®] (Version 9 or higher).

As this is a non-interventional study, no formal statistical testing will be performed and all the analyses will be primarily descriptive in nature. When appropriate and unless otherwise specified, 2-sided 95% confidence intervals (CIs) will be displayed and if p-values are presented, they will be for exploratory purposes only.

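### The primary objective concerns SPIGFD, but the primary treatment-period safety tables pool in off-label and otherwise ineligible legacy participants with no split by label status

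*Protocol*

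**What the plan says.** **Objective and eligibility.** Protocol Section 8.2.1 states the primary objective as "To collect safety data in children and adolescents receiving Increlex® for the treatment of SPIGFD". Section 9.2.3.2 describes eligible participants as those on "treatment with Increlex® therapy for SPIGFD according to the locally approved product information in participating countries". The US limb of Section 9.2.1 is wider: it accepts SPIGFD "or for growth hormone (GH) gene deletion who have developed neutralizing antibodies to GH".

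**Legacy participants.** The note closing Section 9.2.2 (repeated in Table 1 footnote a and Section 9.13) covers anyone enrolled before Amendment #6 who fails any current criterion, with the example of "receiving Increlex® for an indication not covered by the locally approved product information". The investigator receives a letter, and the patient may stay in the registry for post-treatment safety follow-up.

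**Analysis set.** Section 9.7.1 defines the Safety Population as "all participants who have taken the treatment at least once and with at least one follow-up visit", or with any post-treatment safety data. It assigns the primary analysis to that set, and Section 9.7.2.5 builds the primary tables on it for the treatment period.

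**Why label status matters.** Section 7.2 says "Increlex® may increase the risk of benign and malignant neoplasias, particularly in case of off-label use"; the sentence goes on to name doses above the maximum tolerated as well. Section 7.3 reports that benefit-risk "remains positive in its approved indication only", and adds a condition on dose.

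**Off-label use as an AE.** Sections 11.1.1 and 11.1.2.3 require off-label use to be recorded as an AE even when no clinical event occurred.

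**Splits foreseen.** Section 9.7.3 fixes one subgroup, exposure of at least 3 years. Others are optional, and the examples do not include indication or label status. The ENCePP checklist marks stratified analyses as not applicable (item 10.3) and says the same of effect modifiers (Section 8).

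**The concern.** Neoplasia is the adverse event of special interest within the primary endpoint. The protocol itself ties neoplasia risk to off-label use, yet the table reporting it merges on-label and off-label participants. A reader who takes the headline incidence as the answer to Section 8.2.1 would be reading a mixture whose composition is not shown.

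There is a second, mechanical route. Because off-label use is itself recorded as an AE, an off-label participant can count in the all-AE row without having had any clinical event.

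At stake is whether the registry's main safety figure can be attributed to the population named in its objective.

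**Working it through.** The protocol states no sample size, expected incidence or number of off-label participants on this point, so there is no figure to reproduce. The check is a comparison of texts, followed by an algebraic illustration.

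**Step 1: who is in the primary tables**

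| Group | Named in 8.2.1? | In the Safety Population (9.7.1)? |
|---|---|---|
| SPIGFD, label-eligible | Yes | Yes |
| US GH gene deletion with neutralising antibodies (9.2.1) | Not by name | Yes |
| Enrolled before Amendment #6, off-label or otherwise ineligible (note to 9.2.2) | Not if off-label by indication | Yes |

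The legacy note speaks only of post-treatment follow-up, whereas the primary tables use treatment-period data. These participants enter the primary tables because nothing removes the treatment-period data already collected on them. That is an inference from the absence of a filter; the note does not say it.

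The note covers failure of any current criterion. For EU participants the criteria in Section 9.2.2 include a condition or history that raises the risk of neoplasia. The legacy group may therefore contain SPIGFD patients with such a history as well as patients with another indication.

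**Step 2: effect on the incidence of clinical events**

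Let f be the share of off-label or ineligible participants, I the incidence in label-eligible participants and r the risk ratio of the first group to the second.

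Pooled incidence = (1 − f)·I + f·r·I, so pooled / label-eligible = 1 + f(r − 1).

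Both f and r are assumptions:

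| f | r | 1 + f(r − 1) |
|---|---|---|
| 20% | 0.5 | 1 + 0.20 × (−0.5) = 0.90 |
| any | 1 | 1.00 |
| 5% | 2 | 1 + 0.05 × 1 = 1.05 |
| 10% | 3 | 1 + 0.10 × 2 = 1.20 |
| 30% | 3 | 1 + 0.30 × 2 = 1.60 |
| 30% | 5 | 1 + 0.30 × 4 = 2.20 |

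The ratio can be trivial, material or below 1, and the protocol does not allow a choice among the rows. For neoplasia Section 7.2 points towards r above 1, but it gives no rate and names dose alongside off-label use.

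**Step 3: effect on the all-AE row**

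This step needs no risk ratio. Let p be the proportion of label-eligible participants with any AE, and suppose every participant in the share f has an off-label-use record counted as an AE.

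Pooled proportion = (1 − f)·p + f, so the excess over p is f(1 − p).

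The excess lies between 0 (p = 1) and f (p = 0). At f = 10% it is at most 10 percentage points, and at f = 30% at most 30. If nearly everyone has some clinical AE it is close to nil. The event count still rises by at least one per recorded case. The premise is that the AE tables do not set these records aside, and the protocol does not say that they do.

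**The case against.** **An all-treated safety set is conventional, and table layout belongs in the SAP.** The first half stands: the set is legitimate and should stay. The second half stands in part. Section 9.7.2.1 defers detail to a separate SAP, which was not among the documents reviewed, and the subgroup list in 9.7.3 is only illustrative. But the protocol itself fixes the primary set and tables, and its checklist marks stratification as not applicable. An SAP split would supplement the primary table without changing it.

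**Much of this is already visible.** Off-label use is a special situation with its own summary, diagnosis and genetic results are described, and AE listings are by participant. That is true, but none of it yields AE incidence by label status.

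**Stronger readings that the documents do not support:**

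- A reader might infer that the post-treatment tables miss their objective too. The overall long-term objective in Section 8.2.2 covers those who received Increlex® regardless of treatment duration, and an all-treated set fits that wording.
- A reader might infer that the regulator asked for incidence in the approved indication only. Section 7.3 reports a benefit-risk conclusion; the Specific Obligation is described as long-term safety after treatment.
- A reader might treat GH gene deletion as contamination. The US definition of SPIGFD does require "Exclusion of secondary forms of IGF-1 deficiency, such as GH deficiency, malnutrition", which sets it apart. But it is an approved US indication (Section 7.2), Section 9.2.7.1 lists it among the associated aetiologies, and no difference in risk is stated. What remains is a wording mismatch.
- A reader might infer a time drift because off-label participants all predate Amendment #6. Sections 11.1.1 and 11.1.2.3 foresee continuing reports of off-label use, so that is not established.

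**Conclusion.** The point holds for the primary treatment-period tables. The objective names SPIGFD; the analysis set has no indication or eligibility filter; the protocol links neoplasia risk to off-label use; and it makes off-label use an AE in itself. The pooled incidence of neoplasia and of all AEs therefore need not describe labelled SPIGFD patients.

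The size and direction of any difference are unknown. The ratios from 0.90 to 2.20 show what assumed shares and risk ratios would do. They are not estimates, and a reader should not conclude that the headline figure is inflated by any stated amount. Nor would a split by label status isolate indication as the cause, since Sections 7.2 and 7.3 both name dose as well.

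The case for change rests on attribution: the split is cheap, and without it the main safety figure cannot be tied to the population in the objective.

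**What to change.** 1. In Section 9.7.2.5, keep the all-treated total and add two columns: (a) participants meeting current local-label eligibility, with US GH gene deletion identified within it; (b) off-label or otherwise ineligible legacy participants. Answer Section 8.2.1 from the label-eligible SPIGFD part of (a).
2. State how participants are assigned, including how off-label use arising after enrolment is handled.
3. Tabulate off-label-use records separately from clinical AEs, so that label status alone cannot make someone a participant with an AE.
4. Reconcile Sections 8.2.1 and 9.2.3.2, which name SPIGFD only, with Section 9.2.1, which also admits GH gene deletion.
5. The same split in the post-treatment tables (Section 9.7.2.6) is optional.

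The inputs are already foreseen: diagnosis and aetiology (9.2.7.1), reconfirmed eligibility (Table 1 footnote a, 9.13) and off-label reports (11.1.2.3). The work is one classification variable and extra columns. The cost is smaller denominators and wider intervals per column, which will be felt most for rare events such as neoplasia.

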9.2.6 Registry Schedule

The schedule of observations and assessments during the registry are summarised in Table 1.

Table 1 Schedule of Assessments

	Enrolment Visit	Follow-up Visits (in Treatment Period)	Post-treatment Visits
Informed consent ^[a]	X		
Visit date	X	X	X
Eligibility criteria ^[a]	X		
Pregnancy test ^[b]	X		
Demographics	X		
Birth weight and length	X		
Gestational age	X		
Prior heights and sitting heights	X		
Prior weights	X		
Medical history	X		
Personal and family history of neoplasia	X		
Concomitant medications	X	X	X
Parental heights ^[c]	X		
Predicted adult height	X		
Diagnosis of SPIGFD and associated aetiologies	X		
Genetic tests	X		
All AEs, SAEs, AESI, targeted AEs and special situations		X	X ^[d]
Physical examination	X ^[e]	X	X
Height and sitting height	X	X	X
Weight	X	X	X
Pubertal (Tanner) stage	X	X	X
Previous treatments (e.g. GH)	X		
GH concentration ^[f] and stimulation test ^[g]	X		
IGF-1 generation test (if locally applicable) ^[g]	X		
IGF-1 concentration ^[f] ^[g]	X	X	X
IGFBP3 ^[f] ^[g]	X	X	
GHB ^[g]	X		
Bone age, echocardiogram and funduscopic	X	X	X ^[h]
QoL ^[i]	X	X	X
Dose of Increlex® with corresponding dates and compliance	X	X	
Therapy discontinuation		X	
Final Adult Height		X	X

AE = adverse event; AESI = adverse event of special interest; GH = growth hormone; GHBP = growth hormone-binding protein; IGF-1 = insulin-like growth factor-1; IGFBP3 = insulin-like growth factor-binding protein 3; QoL = quality of life; SAE = serious adverse event; SPIGFD = severe primary insulin-like growth factor-1 deficiency.

- a For participants already enrolled in the registry, eligibility must be reconfirmed and a new written informed consent must be obtained for any substantial protocol amendments before implementing them. For any participants enrolled in the registry under previous inclusion/exclusion criteria (i.e. before implementation of Protocol Amendment #6), who would be ineligible according to any of the current inclusion or exclusion criteria, e.g. receiving Increlex® for an indication not covered by the locally approved product information, a letter will be sent to the Investigator to alert him/her about the off-label use of the product (specifically for the risk of neoplasias). The participant could continue to be followed up in the registry for safety data in the post-treatment period
- b A negative pregnancy test must be obtained and documented for all female patients of childbearing potential prior to enrolment/treatment with Increlex®. It is also recommended that all female participants of childbearing potential use adequate contraception during treatment
- c Biological relatives only
- d List of targeted AEs during the post-treatment period is adjusted (see Section 11.1.5)
- e Including dysmorphic features
- f GH, IGF-1 and IGFBP3 levels will be performed by local laboratory (assay has to be documented)
- g Prior to treatment with Increlex®
- h In case of adult height not reached
- i QoL assessments at baseline (start of treatment), at year one, at end of treatment and at Final Adult Height

